4.3.2 Immunogenicity

4.3.2.1 Computed Values for Analysis

In order to appropriately manage extreme values (undetectable responses < the lower limit of quantitation [LLOQ] and \geq the upper limit of quantitation [ULOQ]) for analysis purposes, the following computational rule is applied to the values provided in the clinical database for each blood sample drawn:

- If a value is < LLOQ, then use the computed value LLOQ/2
- If a value is between \geq LLOQ and < ULOQ, then use the value
- If a value is \geq ULOQ, then use the computed value ULOQ

4.3.2.2 Fold-rise

The derived endpoint fold-rise is driven by both baseline and post-baseline computed values and is computed as follows:

- Calculate the fold-rise of values as the ratio of post-baseline computed value divided by baseline computed value

Note: If baseline or post-baseline is missing, then fold-rise is missing.

4.3.2.3 hSBA Vaccine Seroresponse

The derived vaccine seroresponse indicator for hSBA will be “Yes” if:

- hSBA titer is < 1:8 at baseline with a post-baseline hSBA titer \geq 1:16
- or hSBA titer is \geq 1:8 at baseline with a \geq 4-fold increase at post-baseline

4.3.2.4 rSBA Vaccine Seroresponse

The derived vaccine seroresponse indicator for rSBA will be “Yes” if

- rSBA titer is < 1:8 at baseline with a post-baseline rSBA titer \geq 1:32
- or rSBA titer is \geq 1:8 at baseline with a \geq 4-fold increase at post-baseline

4.3.2.5 Efficacy

Not applicable

4.3.3 Derived Other Variables

4.3.3.1 Age for Demographics

The age of a subject in the study was the calendar age in years at the time of inclusion.

4.3.3.2 Duration of a Subject in the Trial

The duration of a subject in the study is computed as follows:

Maximum (date of last visit, date of termination) – (date of Visit 1 of that subject) +1.

4.3.3.3 Duration of the Study

The duration of the study is computed as follows:

Maximum of all subjects (date of last visit, date of termination) – Minimum of all subjects (date of Visit 1) + 1.

5 Statistical Methods and Determination of Sample Size

The statistical analyses will be performed under the responsibility of the Sponsor’s Biostatistics platform using SAS® Version 9.4 software or later.

The results of the statistical analysis will be available in the final clinical study report. For descriptive purposes, the following statistics will be presented:

Table 5.1: Descriptive statistics produced

Baseline characteristics and follow-up description	Categorical data	Number of subjects. Percentage of subjects.
	Continuous data	Mean, standard deviation, quartiles, minimum, and maximum.
Clinical safety results	Categorical data	Solicited: Number and percentage (95% CIs) of subjects. Unsolicited: Number and percentage (95% CIs) of subjects, and number of events.
Immunogenicity results	Categorical data (vaccine seroresponse, \geq 4-fold rise, cutoff)	Number and percentage (95% CIs) of subjects.
	Continuous data (titer / concentration)	Log_{10} : Mean and standard deviation. Anti- Log_{10} (work on Log_{10} distribution, and anti- Log_{10} applied): Geometric mean (GM), 95% CI of the GM. Graphical representation by Reverse Cumulative Distribution Curve (RCDC).

The confidence interval (CI) for the single proportion will be calculated using the exact binomial method (Clopper-Pearson method, quoted by Newcombe (1)). For immunogenicity results, assuming that Log_{10} transformation of the titers follows a normal distribution, at first, the mean and the 95% CI will be calculated on Log_{10} (titers) using the usual calculation for normal distribution (using Student's t distribution with $n-1$ degree of freedom), then antilog transformations will be applied to the results of calculations, in order to provide GMs and their 95% CI.

5.1 Statistical Methods

5.1.1 Hypotheses and Statistical Methods for Objectives

5.1.1.1 Hypotheses

No hypotheses will be tested. Descriptive statistics will be presented.

5.1.1.2 Statistical Methods

Immunogenicity

Immunogenicity results will be described. The reverse cumulative distribution curves (RCDCs) and distribution tables will also be produced for the antibody titers against meningococcal serogroups A, C, Y and W. The parameters will be described with 95% confidence interval (CI).

The 95% CIs of point estimates will be calculated using the normal approximation for quantitative data and the exact binomial distribution (Clopper-Pearson method) for percentages (1).

For geometric mean titers (GMTs) or geometric mean concentrations (GMCs) 95% CIs of point estimates will be calculated using normal approximation assuming they are log-normally distributed.

In summary, descriptive analyses on A, C, Y, and W serogroups will include but not be limited to:

Parameters	rSBA analysis	hSBA analysis
GMC at D0 and D30	X	X
GMT ratio (GMTR) (D30/D0)	X	X
Titer distribution at D0 and D30	X	X
Percentage of subjects with titer \geq 4-fold rise from pre-vaccination (D0) to postvaccination (D30)	X	X
Percentage of subjects with vaccine seroresponse based on D0 and D30 titers	X	X
Percentage of subjects with titer \geq 1:4 at D0 and D30		X
Percentage of subjects with titer \geq 1:8 at D0 and D30	X	X
Percentage of subjects with titer \geq 1:128 at D0 and D30	X	

Tetanus toxoid is contained in the investigational vaccine as a carrier protein. Therefore, blood samples will also be tested for anti-tetanus antibodies by ECL. The following parameters will be assessed:

- Geometric mean concentrations (GMCs) at D0 and D30
- Percentage of subjects achieving seroprotective levels \geq 0.01 IU/mL and \geq 0.1 IU/mL of antibody concentrations to tetanus toxoid at D0 and D30

Safety

Safety results will be descriptive. The 95% CIs of point estimates will be calculated using the exact binomial distribution (Clopper-Pearson method) for percentages

5.1.2 Complementary analysis

Complementary outputs by country will be provided based on main immunogenicity and safety parameters and disposition tables.

The impact of COVID-19 pandemic situation on study conduct will be summarized through impact on visit procedures, study completion and major/critical protocol deviations due to COVID-19.

The subjects impacted by COVID-19 pandemic situation will be defined as the subjects with at least one major/critical protocol deviation due to COVID-19 or who did not complete the study due to COVID-19. If more than 10% of subjects are impacted as per this definition, baseline and demographics characteristics, and the main immunogenicity and safety endpoints will also be summarized in the subsets of subjects impacted/ non-impacted subjects to assess the potential impact of COVID-19 situation on study outcome.

5.2 Analysis Sets

Three analysis sets will be used: the Full Analysis Set (FAS), the Per-Protocol Analysis Set (PPAS), and the Safety Analysis Set (SafAS).

5.2.1 Full Analysis Set

The FAS is defined as the subset of subjects who received at least one dose of the study vaccine and had a valid post-vaccination serology result.

5.2.2 Per-Protocol Analysis Set

The PPAS is a subset of the FAS. The subjects presenting with at least one of the following relevant protocol deviations will be excluded from the PPAS:

- Subject did not meet all protocol-specified inclusion criteria or met at least one of the protocol-specified exclusion criteria
- Subject did not receive vaccine
- Preparation and/or administration of vaccine was not done as per-protocol
- Subject did not provide the post-dose serology sample at Visit 2 in the proper time window (Visit 1 + 30 to 44 days) or a post-dose serology sample was not drawn
- Subject received a protocol-prohibited therapy/medication/vaccine (Category 2 or Category 3)
- Subject's serology sample at Visit 2 did not produce a valid test result (i.e., results for all antigens are missing).
- Subject had another protocol deviation that affected the subject's immune response, as determined by the clinical team before locking the database

This list may not be exhaustive. The above protocol deviations leading to exclusion from the PPAS may be completed if necessary following data review process. The PPAS definition will be finalized before the database lock.

5.2.3 Safety Analysis Set

The SafAS is defined as those subjects who have received at least 1 dose of the study vaccine and have any safety data available.

Safety data recorded for a vaccine received out of the protocol design will be excluded from the analysis and listed separately.

5.2.4 Populations Used in Analyses

All immunogenicity analyses will be performed on the FAS and on PPAS.

All safety analyses will be performed on the SafAS.

5.3 Handling of Missing Data and Outliers

5.3.1 Safety

No replacement will be done. In all subject listings, partial and missing data will be clearly indicated as missing.

5.3.1.1 Immediate

For unsolicited systemic AEs, a missing response to the “Immediate” field is assumed to have occurred after the 30-minute surveillance period and will not be imputed.

5.3.1.2 Causal Relationship

By convention, all events reported at the injection site (either solicited or unsolicited) will be considered as related to the administered product and then referred to as reactions. In a same way, all solicited systemic events pre-listed in the CRF are also considered as related to vaccination and will be considered as reactions.

- For unsolicited systemic AE, missing relationship will be considered as related to study vaccine at the time of analysis.
- The missing relationship to study procedures for SAEs will not be imputed.

5.3.1.3 Intensity

For solicited reactions, missing intensities will be handled as described in [Section 4.3.1.1.1](#). For unsolicited AEs, missing intensities will remain missing and will not be imputed.

5.3.1.4 Start Date and End Date

Missing or partially missing start dates or end dates for unsolicited AEs (including SAEs) will remain missing and not be imputed. If the start date is missing or partially missing, the time of onset will be considered to be missing. Nevertheless unsolicited AEs with missing time of onset will be included in analyses according to the last vaccination (computed according to the [Section 4.3.1.2.3](#)). If either the start date or end date is missing or partially missing, the duration will be considered missing.

Missing or partially missing end dates for ongoing solicited AEs will remain missing and not be imputed.

5.3.1.5 Action Taken

Missing actions taken will remain missing and not be imputed.

5.3.2 Immunogenicity

Missing data will not be imputed. No test or search for outliers will be performed.

5.4 Interim / Preliminary Analysis

No interim / preliminary analyses are planned.

5.5 Determination of Sample Size and Power Calculation

The sample size was arbitrarily chosen to be 280 evaluable subjects. Assuming an attrition rate of approximately 15%, a total of 330 subjects will be included in the study. In order to balance the age of subjects at enrollment, between 50 and 130 enrolled subjects should be ≥ 75 years of age.

Assuming seroprotection rates of 95% or more (rSBA), a sample size of 280 evaluable subjects per group will ensure a 95% CI with a precision of no more than 5.4% (using the exact binomial method).

Assuming seroprotection rates of 75% or more (hSBA), a sample size of 280 evaluable subjects per group will ensure a 95% CI with a precision of no more than 10.5% (using the exact binomial method).

In terms of safety, the planned sample size will allow for identification of common AEs. A sample size of 280 evaluable subjects allows, with 95% probability, for the detection of an AE occurring with a frequency of 1.1% or more, using the rule of threes.

5.6 Data Review for Statistical Purposes

A review of the data has been anticipated through the data review process led by data management before database lock. This review of the data included a statistical review.

5.7 Changes in the Conduct of the Trial or Planned Analyses

5.7.1 Analysis

It is anticipated to have several months of delay to obtain the rSBA results after the LVLS.

Therefore the statistical analysis will be done in two steps as follow:

- A first statistical analysis of the safety and immunogenicity data (except rSBA data) will be done following a database lock with provision. All data included at this stage will be final and won't be modified in later analyses.
- A final statistical analysis will be performed including rSBA data after final database lock.

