5.1 Description of the Overall Study Design and Plan

5.1.1 Study Design

This is a Phase III, open-label, study to describe the immunogenicity and safety of MenACYW conjugate vaccine in potential pilgrims ≥ 56 years of age in Turkey and Lebanon.

Approximately 330 healthy adults will be enrolled in the study to receive a single dose of MenACYW conjugate vaccine.

All subjects will provide pre-vaccination blood samples for immunogenicity assessment at baseline (Visit 1) and at Day (D) 30 (+14-day window) post-vaccination (Visit 2).

Safety data will be collected as follow: Immediate unsolicited systemic adverse events (AEs) will be collected within 30 minutes after vaccination. Solicited AE information will be collected for 7 days after vaccination, unsolicited AE information will be collected from Visit 1 to Visit 2, and SAE information (including adverse events of special interest [AESIs]) will be collected from Visit 1 through Visit 2.

A certificate of vaccination will be given to each subject after vaccination. The individual subject immunogenicity results will be made available to the study investigator once they are available. The investigator will communicate the study results to the individual subjects. Any subsequent clinical intervention, if needed, will be the responsibility of the investigator based on his/ her clinical judgement and outside of the scope of this protocol. If the antibody titers against meningococcal serogroups A, C, W, and Y measured by rSBA did not reach the protective titer of $\geq 1:8$ for one of the serogroups included in the vaccine, the Investigator will advise whether, in light of a potential pilgrimage for Hajj or Umrah in the following 5 years, vaccination with a licensed quadrivalent meningococcal conjugate vaccine will be necessary.

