5.1.5 Planned Study Calendar

The following dates are approximate. The actual dates may differ as, for example, the study will not start until all the appropriate regulatory and ethical approvals have been obtained.

Planned study period - FVFS (first visit, first subject) to LVLS (last visit last subject): April 2019 to July 2021

Planned inclusion period - FVFS to FVLS (first visit, last subject): April 2019 to June 2021

Planned end of study: July 2021

Planned date of final clinical study report: May 2022

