5.2.4 Inclusion Criteria

An individual must fulfill *all* of the following criteria to be eligible for study enrollment:

- 1) Aged ≥ 56 years on the day of inclusion^a
- 2) Informed consent form has been signed and dated
- 3) Able to attend all scheduled visits and to comply with all trial procedures
- 4) Intending to go on a Hajj or Umrah pilgrimage (but not within the next 10 to 12 months after vaccination)

^a “ ≥ 56 years” means from the day of the 56th birthday and older

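### Do the rSBA results come too late for the individual advice that depends on them?

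*SAP*

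**What the plan says.** Protocol 5.1.1 (repeated in the synopsis and in SAP 3.1) describes how individual results are returned: "The individual subject immunogenicity results will be made available to the study investigator once they are available". The investigator then informs the subject. If the rSBA titre is below 1:8 for a serogroup, "the Investigator will advise whether, in light of a potential pilgrimage for Hajj or Umrah in the following 5 years", vaccination with a licensed quadrivalent conjugate vaccine is needed.

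Inclusion criterion 4 (protocol 5.2.4) reads: "Intending to go on a Hajj or Umrah pilgrimage (but not within the next 10 to 12 months after vaccination".

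The calendar in protocol 5.1.5, whose dates are stated to be approximate, gives "Planned inclusion period - FVFS to FVLS (first visit, last subject): April 2019 to June 2021", the last visit of the last subject (LVLS) in July 2021, and "Planned date of final clinical study report: May 2022".

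SAP 5.7.1 states: "It is anticipated to have several months of delay to obtain the rSBA results after the LVLS". It therefore splits the statistical analysis. Safety and all other immunogenicity data are analysed first. For the second step it says: "A final statistical analysis will be performed including rSBA data after final database lock". SAP 5.7.2 records that recruitment was extended because of COVID-19 and that 290 subjects were enrolled.

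**The concern.** The advice rests on one assay, and that assay is reported last. Subjects leave the trial 30 to 44 days after vaccination with a vaccination certificate, and all of them intend to make a pilgrimage at some point. Someone vaccinated in spring 2019 passes the 10 to 12 months in early or mid 2020, while LVLS is planned for July 2021 and the rSBA results follow later still. If the interval was meant to keep subjects from travelling until their titre was known, the dates defeat that purpose for most of the enrolment period. A subject with a low titre could then travel to a setting that the protocol itself describes as prone to outbreaks before hearing about it. The criterion also names a range rather than one figure, so an intended trip at 11 months is eligible on one reading and ineligible on the other.

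**Working it through.** **Check of the planned LVLS.** Last enrolment between 1 and 30 June 2021, plus 30 to 44 days, gives 1 July to 13 August 2021. This agrees with the stated July 2021, given that the dates are approximate.

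**Share of the enrolment calendar.** A subject's interval ends before the results if vaccination date + I < LVLS + delay, with I = 10 or 12 months. The affected share of the enrolment period is

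(LVLS + delay − I − first enrolment) / (last enrolment − first enrolment).

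The documents give months, not days, so several placements within the month were tried. The SAP gives no number of months for the delay, so every delay below is an assumption. The 10-month case corresponds to the planned report date of May 2022.

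*Worked example, lowest share with no delay:* enrolment 30 April 2019 to 30 June 2021 is 792 days. LVLS on 1 July 2021 minus 12 months is 1 July 2020, day 428. 428/792 = 54%.

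*Worked example, highest share with no delay:* enrolment 1 April 2019 to 30 June 2021 is 821 days. LVLS on 28 July 2021 minus 10 months is 28 September 2020, day 546. 546/821 = 67%.

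| Assumed delay after LVLS | I = 12 months | I = 10 months |
|---|---|---|
| 0 months | 54–59% | 62–67% |
| 3 months | 66–70% | 73–78% |
| 6 months | 77–81% | 85–89% |
| 10 months | 92–96% | 100% |

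The first subjects would wait about 27 months (April 2019 to July 2021) plus the delay. So for more than half of the enrolment calendar, the interval ends before the full rSBA data set on any of these assumptions.

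**What the share does not measure.** It is a share of calendar time. Accrual by month is not given, and a pandemic fell within the enrolment period, so even accrual is doubtful. The advice also concerns only subjects below 1:8. The sample-size section assumes at least 95% at or above that level on rSBA. Taking exactly 95%, 290 × 0.05 = 14.5 subjects per serogroup, and at most 4 × 14.5 = 58 if no subject is low for more than one serogroup. With even accrual and the 54% to 89% range, that leaves:

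- if the same subjects are low for all four serogroups: 14.5 × 0.54 ≈ 8 to 14.5 × 0.89 ≈ 13;
- if no subject is low for two: 58 × 0.54 ≈ 31 to 58 × 0.89 ≈ 52.

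How many of these would travel between the end of the interval and the result cannot be derived from the documents.

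**Do the texts conflict?**

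- *Return of results.* Protocol 5.1.1 sets no date, so a late result does not breach it.
- *Horizon of the advice.* It is 5 years. Counted from vaccination, the strictest reading, an April 2019 subject's horizon runs to April 2024. If the result came only in May 2022, about 23 months would remain.
- *Criterion 4.* It describes an intention on the day of inclusion. It does not restrict later travel, and neither document says that it was set to allow for rSBA turnaround.
- *SAP 5.7.1.* It explains why there are two statistical analyses. It does not say that no serum is tested, or that no individual titre is released, before LVLS. Protocol 7.3 makes shipment of sera conditional on monitoring and notification, not on the end of enrolment.

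All four statements can be true together.

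**Does it affect the trial's results?** Antibody is measured at Day 0 and at 30 to 44 days. Both the 10-month and the 12-month mark fall long after the last sample, and so does the return of results. The analysis is descriptive and tests no hypothesis. The loose range could affect the per-protocol set only for a subject whose stated plans fell between the two marks, and the SAP reports immunogenicity on the full analysis set as well.

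**The case for a change.** The best case for a change is that the timing result is robust. The share exceeds half for every delay from 0 to 10 months and for both interval lengths. The rSBA step is the only advice tied to a subject's own titre by a stated threshold. The documents describe no release schedule, no rolling testing, and no way of recontacting people whose participation ended long before. The SAP restates the advice in 3.1 and announces the delay in 5.7.1 without connecting the two. A clarification would cost little and need no extra blood.

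Most of this stands as description: a release timeline is missing, and for early subjects the wait may be long. It does not make a defect in the plan. Individual results returned under 5.1.1 also include hSBA, although hSBA is not the trigger and its analysis also follows LVLS. The rule that would have to be written, to release results as soon as they exist, is already there, and it is not tied to either database lock. Testing in order of vaccination date has a price: several assay runs over more than two years bring run-to-run variation into the rSBA titres and use laboratory capacity. A sponsor may reasonably decline that. With enrolment complete, it could now help only with sera not yet tested.

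**Conclusion.** The concern does not call for a change. On the planned dates, the 10 to 12 months end before the full rSBA results for 54–67% of the enrolment calendar with no delay and 77–89% with an assumed 6-month delay. These figures rest on approximate planned dates and describe calendar time. They become numbers of subjects only under even accrual, which is not documented.

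What they show is an unstated timetable, not a contradiction. The commitment on individual results has no deadline, the advice covers 5 years, and the eligibility interval is not linked to assay turnaround. The sponsor and sites can fill the gap by following the rule already written. The range in criterion 4 is a drafting looseness that cannot influence the antibody measurements. The choice of interval and the content of the advice are for the sponsor and investigators. No estimate, confidence interval or analysis set would be improved by altering the protocol or the SAP on this point.

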5.7.2 Sample size

A total of 330 subjects were initially planned to be enrolled. Due to coronavirus disease 2019 (COVID-19) pandemic, the recruitment period was extended. A total of 290 subjects were actually enrolled in the study.

5.7.3 Reportable medications

Categories of reportable medications were updated and defined as:

- Category 1: medications impacting or that may have an impact on the evaluation of the safety (eg, antipyretics, analgesics, and non-steroidal anti-inflammatory drugs [NSAIDs], systemic steroids/corticosteroids [therapy duration less than 2 weeks], and other immune-modulators) Category 1 medication do not define the Per-Protocol Analysis Set (PPAS).

Note: Topical steroids (inhaled, optic, ophthalmic, nasal, etc.) should not be captured or reported.

Category 1 medications will be reported in the CRF from the day of each vaccination to the end of the solicited and unsolicited follow-up period after each vaccination.

- Category 2: medications impacting or that may have an impact on the immune response and used to define the PPAS; for example:

- Flu vaccines administered within 14 days pre or post each trial vaccination, including the day of the study vaccination visit
- Any vaccine (including COVID-19 vaccine) other than study vaccines (vaccines not described in the Protocol) within the 28 days (4 weeks) preceding or after the trial vaccination, including the day of the study vaccination visit
- Immune globulins, blood or blood-derived products: used in the 3 months preceding the first blood draw and up to the last blood draw
- Immunosuppressive therapy such as immune-suppressors, immune-modulators with immunosuppressive properties, long-term systemic corticosteroids therapy (prednisone or equivalent for more than 2 consecutive weeks) used in the past 3 months preceding the study vaccination and up to the last blood draw, anti-cancer chemotherapy, antiproliferative drugs such as deoxyribonucleic acid (DNA) synthesis inhibitors, or radiation therapy: used in the 6 months preceding the first study vaccination, and up to the last blood draw

Category 2 medications will be reported in the CRF during the study period and up to the last blood draw.

- Category 3: systemic (oral or injectable) antibiotics received within 72 hours preceding each visit for blood draw related to IMP assessment (meningococcal vaccines) and used to define the PPAS, as they may interfere with bioassays used for antibody testing when taken before a blood draw

Category 3 medications will be reported in the CRF for the period of 3 days (72 hours) before each blood draw.

Note: Topical antibiotics (Inhaled, optic, ophthalmic, nasal, etc.) should not be captured or reported.

The information reported in the CRF for each reported medication will be limited to:

- Trade name
- Rationale for the origin of prescription: Whether it was a prophylactic^a medication?

^a Participant's parents/legally acceptable representatives will be required to document all medications received in the diary cards. The sites will focus on only recording the medications belonging to the 3 categories in the other source documents.

Prophylactic medications will be recorded in the Action Taken section of the AE collection tables.

- Medication category (1, 2, or 3)
- Start and stop dates

Dosage and administration route, homeopathic medication, topical and inhaled steroids, as well as topical, ophthalmic, and ear treatments will not be recorded. Topical analgesics should not be applied at the site of vaccination; however, if they are applied inadvertently to the vaccination site,

they should be recorded as a Category 1 medication in this specific instance.

If the participant has received medications other than those listed in Categories 1, 2, and 3, the detailed information will be collected in the source documents only.

Medications given in response to an AE will be captured in the “Action Taken” section of the AE CRF only. No details will be recorded in the concomitant medication CRF unless the medication received belongs to one of the pre-listed categories. Medications will not be coded.

6 References List

1. Newcombe RG. Two-sided confidence intervals for the single proportion: comparison of seven methods. Stat Med. 1998;17(8):857-72.
